6.3.8. Dose Modification

Pembrolizumab will be withheld for drug-related haematological and non-haematological of toxicity \geq Grade 3 including laboratory abnormalities, and severe or life-threatening AEs as per Table 7 below.

Toxicity	Hold Treatment For Grade	Timing for Restarting Treatment	Treatment Discontinuation
Diarrhoea/Colitis	2-3	Toxicity resolves to Grade 0-1.	Toxicity does not resolve within 12 weeks of last dose or inability to reduce corticosteroid to 10 mg or less of prednisone or equivalent per day within 12 weeks.
	4	Permanently discontinue	Permanently discontinue
AST, ALT, or	2	Toxicity resolves to Grade 0-1	Toxicity does not resolve within 12 weeks of last dose.

Increased Bilirubin	3-4	Permanently discontinue (see exception below) ¹	Permanently discontinue
Type 1 diabetes mellitus (if new onset) or Hyperglycemia	T1DM or 3-4	Hold pembrolizumab for new onset Type 1 diabetes mellitus or Grade 3-4 hyperglycemia associated with evidence of beta cell failure.	Resume pembrolizumab when participants are clinically and metabolically stable.
Hypophysitis	2-4	Toxicity resolves to Grade 0-1. Therapy with pembrolizumab can be continued while endocrine replacement therapy is instituted	Toxicity does not resolve within 12 weeks of last dose or inability to reduce corticosteroid to 10 mg or less of prednisone or equivalent per day within 12 weeks.
Hyperthyroidism	3	Toxicity resolves to Grade 0-1	Toxicity does not resolve within 12 weeks of last dose or inability to reduce corticosteroid to 10 mg or less of prednisone or equivalent per day within 12 weeks.
	4	Permanently discontinue	Permanently discontinue
Hypothyroidism		Therapy with pembrolizumab can be continued while thyroid replacement therapy is instituted	Therapy with pembrolizumab can be continued while thyroid replacement therapy is instituted.
Infusion Reaction	3-4	Permanently discontinue	Permanently discontinue
Pneumonitis	2	Toxicity resolves to Grade 0-1	Toxicity does not resolve within 12 weeks of last dose or inability to reduce corticosteroid to 10 mg or less of prednisone or equivalent per day within 12 weeks.
	3-4	Permanently discontinue	Permanently discontinue
	3-4	Permanently discontinue	Permanently discontinue
Renal Failure or Nephritis	2	Toxicity resolves to Grade 0-1	Toxicity does not resolve within 12 weeks of last dose or inability to reduce corticosteroid to 10 mg or less of prednisone or equivalent per day within 12 weeks.

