All Other Drug-Related Toxicity²	3 or Severe	Toxicity resolves to Grade 0-1	Toxicity does not resolve within 12 weeks of last dose or inability to reduce corticosteroid to 10 mg or less of prednisone or equivalent per day within 12 weeks.
	4	Permanently discontinue	Permanently discontinue

Note: Permanently discontinue for any severe or Grade 3 drug-related AE that recurs or any life-threatening event.
¹ For participants with liver metastasis who begin treatment with Grade 2 AST or ALT, if AST or ALT increases by greater than or equal to 50% relative to baseline and lasts for at least 1 week then participants should be discontinued.
² Participants with intolerable or persistent Grade 2 drug-related AE may hold study medication at physician discretion. Permanently discontinue study drug for persistent Grade 2 adverse reactions for which treatment with study drug has been held, that do not recover to Grade 0-1 within 12 weeks of the last dose.

Table 8: Dose modification guidelines for drug-related adverse events

If the toxicity does not resolve to Grade 0-1 within 12 weeks after last infusion, trial treatment should be discontinued at the discretion of the investigator. Participants with a laboratory adverse event still at Grade 2 after 12 weeks may continue treatment in the trial only if asymptomatic and controlled. For information on the management of adverse events, see section 7.

Participants who experience a recurrence of the same severe or life-threatening event at the same grade or greater with re-challenge of pembrolizumab should be discontinued from trial treatment.

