Grades 3 or 4 Grade 3: Prolonged (i.e., not rapidly responsive to symptomatic medication and/or brief interruption of infusion); recurrence of symptoms following initial improvement; hospitalisation indicated for other clinical sequelae (e.g., renal impairment, pulmonary infiltrates) Grade 4: Life-threatening; pressor or ventilatory support indicated	
Stop Infusion.
 
Additional appropriate medical therapy may include but is not limited to:
 
 • IV fluids • Antihistamines • NSAIDS • Acetaminophen • Narcotics • Oxygen • Pressors • Corticosteroids • Epinephrine 
Increase monitoring of vital signs as medically indicated until the participant is deemed medically stable in the opinion of the investigator. Hospitalisation may be indicated.
 
Participant is permanently discontinued from further trial treatment administration.
	
No subsequent dosing

Appropriate resuscitation equipment should be available in the room and a physician readily available during the period of drug administration. For further information, please refer to the Common Terminology Criteria for Adverse Events v4.0 (CTCAE) at http://ctep.cancer.gov
		

Table 8: below shows treatment guidelines for participants who experience an infusion reaction associated with administration of pembrolizumab.

6.5.2. Supportive Care Guidelines for Immune-related Adverse Event (irAE) and Immune-related Events of Clinical Interest (irECI)

Immune-related Adverse events (IrAEs) may be defined as an adverse event of unknown etiology, associated with drug exposure and is consistent with an immune phenomenon. IrAEs may be predicted based on the

nature of the pembrolizumab compound, its mechanism of action, and reported experience with immunotherapies that have a similar mechanism of action. Special attention should be paid to AEs that may be suggestive of potential irAEs. An irAE can occur shortly after the first dose or several months after the last dose of treatment.

If an irAE is suspected, efforts should be made to rule out neoplastic, infectious, metabolic, toxin or other etiologic causes prior to labeling an adverse event as an irAE. Participants who develop a Grade 2 or higher irAE should be discussed immediately with the CI/designee.

Recommendations to managing irAEs not detailed elsewhere in the protocol;

irAE	Withhold/Discontinue pembrolizumab?	Supportive Care
Grade 1	No action	Provide symptomatic treatment

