In addition a set of irAEs have also been classified as immune-related events of clinical interest (irECI) a full list of these can be found in events of clinical interest guidance in Section 7.4. Participants with symptomatic irECIs should immediately stop receiving pembrolizumab and be evaluated to rule out non treatment related causes of the event. Overdose and liver toxicity irECIs irrespective of relationship to the study drug should be reported **within 24 hours** of the investigator being aware of the event to the Sponsor who will in turn notify MSD. If the irECI is determined to be associated please refer to Appendix 4 for the recommendations on the management of these irECIs. If the event is not considered to be associated with the study drug the physician should exercise individual clinical judgment on the event management based on the participant. Any additional questions of the collection or information on management of irECIs should be directed to the Sponsor.

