	Grade 3	
 Report as ECI within 24 hours Withhold pembrolizumab, may restart if Grade 1 or resolved within 12 weeks Recommend Haematology consultation 	
 IV methylprednisone 125mg or Prednisone 1-2mg/kg p.o. (or equivalent) as appropriate. Permanently discontinue pembrolizumab if corticosteroid dose cannot be reduced to prednisone 10mg or less or equivalent per day within 12 weeks.
	Grade 4	
 Report as ECI within 24 hours Discontinue pembrolizumab Recommend Haematology consultation 	
 IV methylprednisone 125mg or Prednisone 1-2mg/kg p.o. (or equivalent) as appropriate.
Hepatic – Drug induced Liver Injury (DILI). Please refer to ECI guidance for definitions of (DILI)	Grade 1 (Asymptomatic)	
 No action 	
 Intervention not indicated
	Grade 2	
 Report as ECI within 24 hours Withhold Pembrolizumab if AST or ALT >3.0 to 5.0 X ULN and/or total bilirubin is >1.5 to 3.0 X ULN Monitoring Liver function until values return to baseline 	
 0.5-1mg/kg/day methylprednisone 125mg or oral equivalent. LFT grade 1 or less initiate steroid taper for no less than 4 weeks. Consider prophylactic antibiotics and resume pembrolizumab. Permanently discontinue pembrolizumab if dose cannot be reduced to prednisone 10mg or less or equivalent per day within 12 weeks. Permanently discontinue pembrolizumab for patients with liver mets who begin treatment with grade 2 elevation of AST or ALT and AST or ALT increase ≥50% relative to baseline and lasts ≥ 1 week.
	Grade 3	
 Report as ECI within 24 hours Discontinue pembrolizumab if AST or ALT > 5.0 X ULN and/or total bilirubin is >3.0 X ULN Consider consultation and biopsy to establish etiology 	
 High dose IV glucocorticosteroids for 24-48hours. Symptoms grade 1 or less initiate steroid taper for no less than 4 weeks prednisone 1 to 2 mg/kg/day or dexamethasone 4mg every 4 hours. If serum transaminase levels do not decrease or symptoms worsen please refer to additional guidance in the ECI guidance document.

			
 Permanently discontinue pembrolizumab if dose cannot be reduced to prednisone 10mg or less or equivalent per day within 12 weeks.

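### Hepatic Grade 2: section 6.3.8 lets a resolved patient still above 10 mg prednisone restart, Appendix 4 stops that patient for good, and the 6.3.8 laboratory allowance is left unclear

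*Combined protocol and SAP*

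**What the plan says.** Both texts reach the same patient. The table in section 6.3.8 covers drug-related AST, ALT or bilirubin elevation. Section 7.4 lists hepatitis and transaminase elevation of Grade 2 or above among the immune-related events of clinical interest. For such events judged drug-associated, section 6.5.2 says "please refer to Appendix 4 for the recommendations on the management of these irECIs".

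- **Section 6.3.8, hepatic Grade 2.** Hold, and restart once the event is at Grade 0-1. The discontinuation cell reads in full: "Toxicity does not resolve within 12 weeks of last dose". It has no steroid criterion.
- **Appendix 4, hepatic Grade 2.** Hold, give steroids, and start a taper of at least 4 weeks once liver tests are at Grade 1 or less. The cell then says "resume pembrolizumab. Permanently discontinue pembrolizumab if dose cannot be reduced to prednisone 10mg or less or equivalent per day within 12 weeks". It has no 12-week limit on non-resolution.
- **Section 6.3.8, text after the table.** If a toxicity has not reached Grade 0-1 by 12 weeks, "trial treatment should be discontinued at the discretion of the investigator". The next sentence adds: "Participants with a laboratory adverse event still at Grade 2 after 12 weeks may continue treatment in the trial only if asymptomatic and controlled".
- **Section 6.5.2.** "Participants who develop a Grade 2 or higher irAE should be discussed immediately with the CI/designee". Its hepatitis paragraph refers back to the preceding guidelines and gives no grade or time limit of its own.

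**The concern.** This is a rule for restarting or stopping a drug after liver injury. A site that follows 6.3.8 alone can re-dose a patient whom Appendix 4 says must stop permanently, and it would be compliant with the text it read. No sentence says which criterion governs, or that the stricter one should be applied.

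The laboratory allowance adds a second uncertainty. Raised AST, ALT and bilirubin are laboratory findings, so an investigator could reasonably apply it to them. The hepatic row above it states a stop with no such exception. What is at stake is consistent handling of a liver toxicity across 15 to 24 sites.

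**Working it through.** No plan figure enters this point. The check is a comparison of texts.

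**Step 1. Is the missing steroid criterion a pattern or an exception?** Seven rows of the 6.3.8 table stop for non-resolution within 12 weeks: colitis 2-3, hepatic 2, hypophysitis 2-4, hyperthyroidism 3, pneumonitis 2, renal 2 and all other toxicity 3. Six of them add inability to get the steroid down to 10 mg. Only hepatic Grade 2 does not (7 − 6 = 1). That looks like an omission.

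**Step 2. Trace each state at 12 weeks.** The assumptions are that both 12-week clocks run together (6.3.8 counts from the last dose; Appendix 4 gives no starting point) and that a dose still above 10 mg counts as one that cannot be reduced. The question is whether drug may be given.

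| State at 12 weeks | 6.3.8 row | Appendix 4 row | Same on dosing? |
|---|---|---|---|
| Resolved, 10 mg or less | may restart | may resume | yes |
| Resolved, above 10 mg | may restart | permanent stop | **no** |
| Unresolved, 10 mg or less | stop | still on hold | yes, no drug |
| Unresolved, above 10 mg | stop | permanent stop | yes, no drug |

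The rows differ on dosing in 1 of 4 states. In the third, Appendix 4 ties resumption to Grade 1 or less, so the patient gets no drug under either text. What is missing there is an end to the hold.

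**Step 3. Can the discordant state occur?** Appendix 4 requires a taper of at least 4 weeks from resolution. A taper begun after week 8 is still running at week 12 (8 + 4 = 12). Whether the dose is then above 10 mg depends on the schedule, so the state is possible but its frequency is unknown.

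**Step 4. Does another rule block the restart?** Section 6.4.2 prohibits glucocorticoids but exempts those given for an immune-related event of clinical interest, so it does not. The general immune-event table in 6.5.2 has a steroid criterion for Grades 3 and 4 only.

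**Step 5. Add the laboratory allowance.** If it covers AST, ALT and bilirubin, an asymptomatic, controlled patient still at Grade 2 may continue. The hepatic row of 6.3.8 says stop. Appendix 4 says hold at 10 mg or less and permanent stop above it. If the allowance does not cover them, Step 2 stands unchanged. The text does not say which reading is meant.

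**The case against.** The best reply is that the two rows can both be obeyed. Section 6.3.8 permits restart and does not order it, and Appendix 4 adds a further condition, so an investigator who always takes the stricter rule breaches neither. Grade 2 immune events must also be discussed at once with the chief investigator or designee, Appendix 4 is described as recommendations, and it cites separate guidance on these events that is not in the documents. These points limit the risk and stand to that extent. They do not supply the criterion: the discussion requirement names none, no text says to take the stricter rule, and nothing can be assumed about the guidance.

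It is also fair that Appendix 4's silence on non-resolution is not a void. The hepatitis paragraph of 6.5.2 points back to guidelines that arguably include a 12-week note, under which discontinuation should be considered after discussion. That is softer than the stop in 6.3.8, so it narrows the gap without closing it.

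A reader might infer a similar conflict at hepatic Grade 3, because the Appendix 4 supportive-care cell ends with the same taper-failure stop and could seem to allow restart after a successful taper. The documents do not support that. The action cell says "Discontinue pembrolizumab if AST or ALT > 5.0 X ULN and/or total bilirubin is >3.0 X ULN", the 6.3.8 row says "Permanently discontinue (see exception below" and points to its footnote, and no text permits restart after a taper. The bullet is redundant wording. There is one narrower difference. A patient with liver metastases who starts at ALT 4.5 × ULN and rises to 5.5 × ULN has a rise of (5.5 − 4.5)/4.5 = 22%, below the 50% in the 6.3.8 footnote, yet is above the 5.0 × ULN limit in Appendix 4. Whether that exception should apply at Grade 3 is a clinical decision for the sponsor.

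**Conclusion.** The point holds for hepatic Grade 2. The two rows give different answers on dosing in one state, resolved to Grade 0-1 but above 10 mg prednisone at 12 weeks. Separately, the laboratory allowance contradicts the hepatic row's stop and the Appendix 4 hold if it is meant to cover AST, ALT and bilirubin. A reader might infer that the allowance is detached from the hepatic row. It is the closing text of the same section, directly under the table, which is why its scope needs stating.

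The conclusion rests on the two assumptions in Step 2 and on the documents supplied. The size is small: a minor safety-text correction, with no patient count claimed and no effect on sample size, power or analyses.

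**What to change.** At the next amendment:

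1. In the 6.3.8 hepatic Grade 2 row, add the steroid criterion that the other six rows carry (dose not brought down to 10 mg per day of prednisone equivalent, or less, within 12 weeks).
2. In the Appendix 4 hepatic Grade 2 row, add the stop for non-resolution within 12 weeks of the last dose.
3. After the 6.3.8 table, state whether the Grade 2 laboratory allowance applies to AST, ALT and bilirubin.

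A general statement that 6.3.8 prevails over Appendix 4 would be the wrong remedy. It would loosen stricter appendix rules such as neurologic Grade 3, which Appendix 4 discontinues and the all-other row of 6.3.8 would let restart. Nor should the liver-metastasis footnote be carried into the Appendix 4 Grade 3 cell as an editorial change.

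The cost is wording in two table rows and one clarifying sentence, with no extra data or patients. The downside is that a few patients slow to taper would stop drug under 6.3.8, as they already must under Appendix 4.

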5.3. Clinical Procedures/Assessments

5.3.1. Adverse Event (AE) Monitoring

The investigator or qualified designee will assess each participant for potential new or worsening AEs at specified visits as defined in the schedule of study assessments (Table 2) or more frequently if clinically indicated. Adverse experiences will be graded and recorded from randomisation until the Safety follow-up. (Any clinical abnormalities found between informed consent and randomisation will be documented on the medical history form). AEs will be graded according to NCI CTCAE Version 4.0 and LENT SOMA radiation toxicity grading system (see Appendices Section). Toxicities will be characterised in terms regarding seriousness, causality, toxicity grading, and action taken with regard to trial treatment.

All AEs of unknown etiology associated with pembrolizumab exposure should be evaluated to determine if it is possibly an event of clinical interest (ECI) of a potentially immunologic etiology (irAE). See Section 7

regarding the identification, evaluation and management of AEs of a potential immunological etiology. Please refer to Section 7 for detailed information regarding the assessment and recording of AEs.

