6.5. Rescue Medications & Supportive Care

6.5.1. Supportive Care Guidelines

Participants should receive appropriate supportive care measures as deemed necessary by the treating investigator including but not limited to the items outlined below:

6.5.1.1. Diarrhoea:

Participants should be carefully monitored for signs and symptoms of:

- Enterocolitis (diarrhoea, abdominal pain, blood or mucus in stool, with or without fever)
- Bowel perforation (peritoneal signs and ileus).

In symptomatic participants, infectious etiologies should be ruled out, and if symptoms are persistent and/or severe, endoscopic evaluation should be considered.

- In participants with severe enterocolitis (Grade 3):
 - Pembrolizumab will be **permanently discontinued** and treatment with systemic corticosteroids should be initiated at a dose of 1 to 2 mg/kg/day of prednisone or equivalent. When symptoms improve to Grade 1 or less, corticosteroid taper should be started and continued over at least 1 month.
- In participants with moderate enterocolitis (Grade 2):
 - Pembrolizumab should be **withheld** and anti-diarrhoeal treatment should be started. If symptoms are persistent for more than one week, systemic corticosteroids should be initiated (e.g., 0.5 mg/kg/day of prednisone or equivalent). When symptoms improve to Grade 1 or

less, corticosteroid taper should be started and continued over at least 1 month. Guidelines for continuing treatment with pembrolizumab can be found in Appendix 5.

- All participants who experience diarrhoea should be advised to drink liberal quantities of clear fluids. If sufficient oral fluid intake is not feasible, fluid and electrolytes should be substituted via IV infusion.

6.5.1.2. Nausea/vomiting:

Nausea and vomiting should be treated aggressively, and consideration should be given in subsequent cycles to the administration of prophylactic antiemetic therapy according to standard institutional practice. Participants should be strongly encouraged to maintain liberal oral fluid intake.

6.5.1.3. Anti-infectives:

Participants with a documented infectious complication should receive oral or IV antibiotics or other anti-infective agents as considered appropriate by the treating investigator for a given infectious condition, according to standard institutional practice.

6.5.1.4. Immune-related adverse events:

Please see Section 6.5.2 below regarding diagnosis and management of adverse experiences of a potential immunologic etiology.

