	Grade 4	
 Report as ECI within 24 hours Discontinue pembrolizumab 	
 Manage as per grade 3
Neurologic	Grade 1 (Asymptomatic)	
 No action 	
 Intervention not indicated
	Grade 2	
 Report as ECI within 24 hours Consider withholding pembrolizumab Consider Neurology consult and biopsy for diagnosis. 	
 Consider 1-2mg/kg daily of prednisone as appropriate Permanently discontinue pembrolizumab if dose cannot be reduced to prednisone 10mg or less or equivalent per day within 12 weeks.
	Grade 3 and 4	
 Report as ECI within 24 hours Discontinue pembrolizumab Obtain Neurology consultation Consider biopsy for diagnosis. 	
 1-2mg/kg daily of prednisone or equivalent. If condition worsens consider IVIG or other immunosuppressive therapies Symptoms grade 1 or less, initiate steroid taper for no less than 4 weeks.
Ocular	Grade 1 (Asymptomatic)	
 No action 	
 Intervention not indicated
	Grade 2	
 Report as ECI within 24 hours Evaluation by ophthalmologist recommended 	
 Topical steroids – 1%prednisolone acetate suspension and iridocyclitics Permanently discontinue IF symptoms persist despite treatment.
	Grade 3	
 Report as ECI within 24 hours Evaluation by ophthalmologist recommended Withhold pembrolizumab & consider discontinuation. 	
 1-2mg/kg of prednisone daily. Symptoms grade 1 or less initiate steroid taper for no less than 4 weeks. Permanently discontinue pembrolizumab if dose cannot be reduced to prednisone 10mg or less or equivalent per day within 12 weeks.
	Grade 4	
 Report as ECI within 24hours Evaluation by ophthalmologist recommended Permanently discontinue pembrolizumab 	
 Manage as per grade 3
Renal	Grade 1 (Asymptomatic)	
 No action 	
 Intervention not indicated

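### For a first Grade 3 immune neurologic event, the Section 6.3.8 dose table permits restart after recovery while Appendix 4 says discontinue, and nothing says which prevails

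*Combined protocol and SAP*

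**What the plan says.** **Appendix 4.** The neurologic entry advises considering a hold at Grade 2. At Grade 3 and 4 it reads "Report as ECI within 24 hours Discontinue pembrolizumab Obtain Neurology consultation". The supportive-care column beside it covers steroids, other immunosuppression and tapering, and says nothing about restarting.

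**Section 6.3.8, dose-modification table.** There are named rows for colitis, liver tests, diabetes, hypophysitis, thyroid disorders, infusion reactions, pneumonitis and renal events, but none for neurologic events. A residual row takes all other drug-related toxicity. For Grade 3 or severe events, that row holds the drug until "Toxicity resolves to Grade 0-1" and stops it only if the event has not resolved, or steroids cannot be reduced, within 12 weeks. At Grade 4 it stops the drug permanently.

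**Text around that table.** The note below it says "Permanently discontinue for any severe or Grade 3 drug-related AE that recurs or any life-threatening event". The last sentence of the section says that patients with a recurrence of the same severe or life-threatening event "at the same grade or greater with re-challenge of pembrolizumab should be discontinued from trial treatment". For management the section says "For information on the management of adverse events, see section 7".

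**Other routes.** Section 5.3.1 also points to Section 7 "regarding the identification, evaluation and management of AEs of a potential immunological etiology". Section 6.5.1.4 points elsewhere: "Please see Section 6.5.2 below regarding diagnosis and management of adverse experiences of a potential immunologic etiology". Section 6.5.2 then says "If the irECI is determined to be associated please refer to Appendix 4 for the recommendations on the management of these irECIs". Section 7.4 lists autoimmune neuropathy, Guillain-Barre syndrome, demyelinating polyneuropathy and myasthenic syndrome as events of clinical interest at any grade.

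**The concern.** The dose-modification table is the natural place for a site to look when deciding whether to give the next infusion. For a patient who has recovered from a first Grade 3 immune neurologic event, that table allows treatment to resume. The event-specific guidance in Appendix 4 takes the same patient off the drug.

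At stake is re-exposure to pembrolizumab after a severe immune neurologic event for which the protocol's own specific guidance ends treatment. The possible harm to that patient is serious even if such events are rare. Sites could also manage the same event differently, each with a text in the protocol to support it.

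**Working it through.** No arithmetic applies beyond a count. The check sets the two texts side by side, settles what each one means, and follows the cross-references.

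**1. The rules by grade**

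| Immune neurologic event, drug-related | Section 6.3.8 (residual row and note) | Appendix 4, neurologic | Agree? |
|---|---|---|---|
| Grade 3, first occurrence, at onset | Hold | Discontinue | Yes: drug stopped |
| Grade 3, first occurrence, recovered to Grade 0-1 within 12 weeks with steroids reduced | Restart permitted | No restart option | **No** |
| Grade 3, recurrence | Permanent stop | Discontinue | Yes |
| Grade 4 | Permanent stop | Discontinue | Yes |

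The disagreement is confined to the second line. The note under the table makes the Grade 3 permanent stop depend on recurrence, and the closing sentence of Section 6.3.8 presupposes that re-challenge after a severe event can happen. Neither closes off restart after a first event.

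**2. Does discontinue in Appendix 4 mean a permanent stop?** Most naturally, yes, for this entry:

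- Where Appendix 4 contemplates a restart it generally uses withhold and often adds that the drug may be restarted (Grade 2 pneumonitis, Grade 2 colitis, Grade 3 hyperthyroidism, Grade 2 and 3 haematologic events).
- Its plain discontinue for Grade 3-4 pneumonitis, Grade 4 colitis and Grade 3-4 renal events corresponds to an explicit permanent stop in Section 6.5.2.
- The neurologic entry itself moves from considering a hold at Grade 2 to discontinue at Grade 3.

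The usage is not uniform. Grade 4 ocular events carry the word permanently, and the Grade 3 hepatic entry says discontinue and then attaches a permanent stop to failure to reduce steroids within 12 weeks. The neurologic Grade 3-4 entry has no such condition.

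**3. Is the neurologic case unusual?** Appendix 4 has 13 categories. Four say discontinue at Grade 3: pneumonitis, hepatic, neurologic and renal. The other 13 − 4 = 9 say withhold, hold, consider stopping, or continue. Compared with the Section 6.3.8 table:

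- Pneumonitis: own row, Grade 3-4 permanent stop.
- Hepatic: own row, Grade 3-4 permanent stop, subject to the table's footnote for patients with liver metastases. The Appendix 4 wording has the conditional element noted in step 2, so this match is less clean than the others.
- Renal: Grade 3-4 permanent stop. The line is displaced in the text as read from PDF, but the nephritis paragraph in Section 6.5.2 confirms the rule.
- Neurologic: no row.

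So 3 of the 4 have a row that stops the drug at Grade 3, and neurologic is the only one without. The pattern looks like an omission, though the documents do not say.

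**4. Where do the cross-references lead?**

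- Section 6.3.8 → Section 7. Section 7 classifies and reports these events. It has no hold, restart or stop rule for them and does not mention Appendix 4.
- Section 5.3.1 → Section 7, with the same result.
- Section 6.10.1, for unacceptable adverse experiences → Section 6.2, which is the radiotherapy section.
- Section 6.5.1.4 → Section 6.5.2 → Appendix 4. This route works, but Section 6.5.2 describes the Appendix 4 content as recommendations and does not rank it against the dose table. Its event-specific paragraphs do not name neurologic events.

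**The case against.** The strongest reply is that the protocol already handles the event. Section 7.4 makes these neurologic conditions events of clinical interest at any grade. Section 6.5.2 stops the drug immediately when such an event is symptomatic, sends drug-associated ones to Appendix 4, and wants any immune-related event of Grade 2 or higher discussed at once with the chief investigator or designee. Appendix 4 can be found by its title. Section 6.5.2 also limits its own general table to events not covered elsewhere, which suggests that specific text should outrank residual text. On that reading the named neurologic entry governs.

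Much of this stands. The route exists, and the safeguards make an unintended re-challenge less likely. They do not settle the disputed step. The immediate stop is for evaluation and does not say whether treatment may resume after recovery. The discussion with the chief investigator sets no rule, and both parties would have the same two texts before them. Specific over general is a sensible reading, but for the Section 6.3.8 table it is an inference.

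A reader might infer that the protocol requires re-challenge, or that a site following Appendix 4 departs from the protocol. It does neither: the table permits restart without obliging it. A reader might also infer a conflict at Grade 4, because the general table in Section 6.5.2 says withhold at Grade 3 and 4. That table excludes events detailed elsewhere, and Appendix 4 details these.

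**Conclusion.** The inconsistency is real and narrow. It concerns one toxicity class, one grade and a first occurrence, and only the question of restart after recovery. The texts agree on the initial stop, on recurrence and on Grade 4. The route through Section 6.5.2 limits the risk but does not correct a stated dosing rule that permits what the event-specific guidance rules out.

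The conclusion rests on two readings: that an event without its own row belongs in the residual row, and that discontinue in the neurologic entry is meant as permanent. The first follows from the table's layout. The second is the more natural reading but not beyond argument, given the uneven wording elsewhere in Appendix 4.

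The number of patients affected cannot be worked out from the documents. Endpoints, power and analysis are untouched. A minor patient-safety consistency correction is the right weight.

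A reader might also infer that the protocol needs a general rule giving the stricter of the two texts precedence. This finding does not support that. Such a rule would change dosing for hypophysitis, Grade 2 haematologic events, Grade 2 severe skin reactions and non-improving Grade 1 events in the other category. In each of these Appendix 4 withholds where the table allows continuation, leaves a hold to discretion or has no hold. Those are separate clinical decisions, and no case for them is made here.

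**What to change.** Add one row to the Section 6.3.8 dose-modification table: *Immune-related neurologic events listed in Section 7.4, Grade 3-4: permanently discontinue (see Appendix 4).* The row carries the Appendix 4 instruction into the table and supplies the missing cross-reference. It leaves other toxicities as they are.

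The cost is one line in a protocol amendment, with no change to design, sample size or analysis. The downside is that re-challenge after a recovered Grade 3 immune neurologic event would no longer be available. If the sponsor wants to keep that option, the Appendix 4 entry should be changed to say so, with the conditions for restart.
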